## **Participants, inclusions- and exclusions criteria**

There are 24-48 children on each of the DCSH. They have a continuously admission of children in the age range 7-14 years, and every child is offered a 10 weeks residential stay. From september 2018 about 600 children (boys and girls) will be recruited from two DCSH.

Inclusions criteria:

- Boys and girls in a 10-week residential stay at the DCSH in the age of 7-14 year.
- Informed consent from parents/legal guardian.
- Willingness to participate in training and tests.

Exclusions criteria:

- Participants, of which the scientists do not find, suited to follow the procedures of the protocol and the program for training and testing.

Participants can at all times choose to withdraw from tests, if this is desired or necessary due to illness or injury. All children at the DCSH participate in the training as part of the scheduled program.

The specific reasons to include individuals, who cannot give informed consent, are group C, cf. Comity law §19: “That the project can only be completed by including individuals, whom are in the specific age

group, illness or condition, and that the project have a direct possibility to transfer large positive advantages to the patient population that consist of the same age group, illness or condition as the participant, and that the project involve minimal risk and inconvenience for the child or the young participant". The project can give valuable information on health-related training effects and form the foundation for physical activity recommendations for overweight children in Denmark. The project is also useful for any specific participant, as participants and parents, besides for the training, achieve knowledge about physical capacity and health. Furthermore, there are minimal risks for the participant in relation to the tests, measurements and training.

### Statistic and power calculation

The primary outcome of the project is fat percentage, and among the most important secondary outcomes are aerobic fitness, health-knowledge and well-being. The power calculation is based on the result of the pilot project (Ørntoft et al. 2016). The power calculation is measured with t-test. Some variables are expressed in table below and are based on the development on variables from the pilot study and a study with children from the same age group as on the DCSH (Bendiksen et al. 2014). The calculations are based on a power of 0.80 and p-value of 0.05.

Calculation of number of participants (N) in relation to the evaluation on the DCSH standard program and the assessment of activity and health-program (HIHE).

Power calculation	Intervention group (HIHE)	Standard group	IG vs SG	Delta IG SG Sample size
Fat percentage, intervention period	-9.6 (4.2)	-8.9 (3.7)	-0.6 (2.3)	232
Fat percentage, follow- up period	5.0 (13.4)	8.4 (12.9)	-3.3 (11.2)	182
Aerobic fitness	148 (63)	-106 (83)	254 (85)	4
Health-knowledge	11.9 (23.5)	2.6 (23.7)	9.4 (23.5)	100
Muscle mass	0.6 (0.7)	0.5 (0.9)	0.6 (0.8)	29

Number of participants, 1:1 randomisation	Number of participants with 75% at post-tests
464	580
364	455
8	10
200	250
58	73

The calculations are based upon a randomisation of 1:1, 50% of the participants participate in the standard program. Based on the power calculation, the total number of participants is estimated to be approx. 600 children. This is under the consideration of a completion rate of 75%.

All outcomes will be analyzed by means of linear mixed models including two-way interaction between intervention (standard and intervention) and time (before and after) as fixed effect and child and site as random effects (to account for differences between children and between sites, respectively). Adjustment for age, sex, and possibly other covariates/confounders will also be included as fixed effects in the models.

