## Method

### Design

Approximately 600 boys and girls in the age 7-14 years are recruited from two DCSH. The design is a cross-over design at DCSH level over a two-year period with two intervention groups: A standard group (with the standard program (SG)) and a standard + HIHE (SG+). In SG+ the children will, in addition to the standard program, play recreational football 2x45 min. a week. In SG the children will perform the planned activities according to the schedule. The training in SG+ will be performed indoor or outdoor on grass (depending on the facilities on the specific DCSH) with different football exercises (dribbling, ball control, passes etc.) and small-sided games with high intensity (3v3 to 5v5) on two goals. All training sessions take place on the DCSH or in the immediate vicinity of the DCSH. Every week, a specific football skill is connected with a health message. E.g., the skill of passing the ball to each other is related to respect of each other and avoid bullying.

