### **Recruitment of participants**

The participants are recruited from two DCSH. In the project's cooperation agreement, it is specified that two of the DCSH change practice for one year. In this manner, all the children at the two DCSH are participating in the HIHE intervention, regardless of their participation in tests. To investigate the standard program, all tests will be carried out at both of the DCSH for one year. After the first year the two participating DCSH change intervention group. Alongside the general information about the stay at the DCSH, written information about the study will be provided and subsequently an oral information meeting / parent meeting cf. the description below.

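### The 232 per arm for fat percentage rests on an unexplained SD of 2.3, below both arm SDs in its own row (4.2 and 3.7); with the arm SDs, power at 225 completers per arm is about 36% (difference 0.6) to 46% (0.7), not 80%

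*Combined protocol and SAP*

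**What the plan says.** The section on statistics and power states: "The primary outcome of the project is fat percentage". On the method it says "The power calculation is measured with t-test" and "The calculations are based on a power of 0.80 and p-value of 0.05". Allocation is 1:1, and "50% of the participants participate in the standard program". The inputs are attributed to a pilot study and a second study in children; no derivation is given for individual cells.

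The row for fat percentage over the intervention period reads:

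- HIHE arm: -9.6 (4.2)
- Standard arm: -8.9 (3.7)
- Comparison: -0.6 (2.3)
- Sample size: 232, or 464 in total

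This is the largest requirement in the table and leads to the planned total of about 600 at 75% completion. The brackets are not labelled, and the unit of the entries is not stated.

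The planned analysis is a linear mixed model with an intervention-by-time interaction and random effects for child and site. On covariates it says: "Adjustment for age, sex, and possibly other covariates/confounders will also be included as fixed effects in the models". Adjustment for the baseline value is not named.

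**The concern.** A two-sample t-test is sized on the spread of the outcome within each arm. The row gives that spread twice, as 4.2 and 3.7, and then uses 2.3. Required numbers grow with the square of the SD, so moving from 2.3 to about 4 nearly triples them.

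This row carries the primary outcome and sets the size of the trial. If the arm SDs are the relevant ones, a true difference of 0.6 to 0.7 would be missed more often than found. A reader who trusts the stated 80% would then take a null result as stronger evidence against such a difference than it is.

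**Working it through.** **Inputs, all from the power section.** Differences of 0.6 (comparison column) and 0.7 (9.6 - 8.9, the gap between the arm means); SDs of 4.2, 3.7 and 2.3; alpha 0.05; power 0.80; 600 children with 75% completion, so 600 x 0.75 / 2 = 225 completers per arm. Sidedness is not stated. Two-sided reproduces the table; one-sided would give 182 for this row.

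**1. Reproducing 232.** By the normal approximation, n per arm = 2 x (1.960 + 0.842)^2 x (SD/difference)^2 = 15.70 x (2.3/0.6)^2 = 231. The exact t-test gives 231.6, rounded up to 232. So 2.3 was entered as the common within-arm SD.

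**2. What the arm cells imply.** Pooled SD = sqrt((4.2^2 + 3.7^2)/2) = sqrt(15.665) = 3.96. With every cell at its rounding limit:

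- sqrt((4.15^2 + 3.65^2)/2) = 3.91
- sqrt((4.25^2 + 3.75^2)/2) = 4.01

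Rounding cannot reach 2.3. A pooled SD lies between the two arm SDs whatever the split of children.

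**3. Are the brackets SDs?** The health-knowledge row has arms 23.5 and 23.7 (pooled 23.6), comparison 23.5 and difference 9.4. The t-test gives 99.1, listed as 100. The muscle-mass row has arms 0.7 and 0.9 (pooled 0.81), comparison 0.8 and entered difference 0.6. The t-test gives 28.9, listed as 29. Both rows use the bracket as an SD close to the pooled arm value.

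**4. Could 2.3 be a paired SD?** The protocol says "The design is a cross-over design at DCSH level over a two-year period", and "After the first year the two participating DCSH change intervention group". It is the houses that cross over. On the children it says "every child is offered a 10 weeks residential stay", so the arms are different children. A paired SD of 2.3 would need a correlation of (4.2^2 + 3.7^2 - 2.3^2)/(2 x 4.2 x 3.7) = 26.04/31.08 = 0.84 between them. A paired t-test with 0.6 and 2.3 would also need about 117 pairs (117.3), not 232 per arm.

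**5. Does the planned model supply the reduction?** For complete before-and-after pairs, the intervention-by-time term with a random child effect is the difference in mean change. Covariates entered as main effects do not alter its standard error. In one simulated data set (225 per arm, complete pairs, no site effect) that standard error was 0.3815 without age and sex, 0.3815 with them, and 0.3815 for the t-test on change. To bring 3.96 down to 2.3, covariates would have to explain 1 - (2.3/3.958)^2 = 66% of the variance in change.

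**6. Power at 225 per arm.** The standard error is SD x sqrt(2/225) = SD x 0.0943. For SD 3.96 it is 0.373, so 0.6/0.373 = 1.61, and approximate power is Phi(1.61 - 1.96) = 36%. Exact two-sided t-test values:

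| SD used | Power, difference 0.6 | Power, difference 0.7 |
|---|---|---|
| 2.3 | 79% | 90% |
| 3.7 (smaller arm SD) | 40% | 52% |
| 3.96 (pooled) | 36% | 46% (0.465) |
| 4.2 (larger arm SD) | 33% | 42% |

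- Over the rounding limits of the pooled SD, power is 35-37% for 0.6 and 46-47% for 0.7.
- The difference detectable with 80% power is 0.61 with SD 2.3 and 1.05 with SD 3.96.
- The largest SD that still gives 80% is 2.27 for 0.6 and 2.64 for 0.7, both below either arm SD.
- With SD 3.96, 80% power would need 685 per arm for 0.6 or 503 for 0.7.

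**7. The follow-up fat row.** Difference 3.3 with SD 11.2 gives 181.8, listed as 182. The arms, 13.4 and 12.9, pool to 13.15, so 11.2 is again below both. With 13.15 the need is 250.3 per arm (3.3) or 235.9 (3.4, the gap between the arm means), and power at 225 per arm is 76% or 78%. The same inconsistency is present here, with little effect.

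**The case against.** The strongest reply is that nothing has been miscalculated: 232 follows from 0.6 and 2.3, and the real defect is an undocumented input. The comparison column also need not be a pooled SD. In the aerobic-fitness row it is 85, above both arms (63 and 83, pooled 73.7), and in the muscle-mass row the entered difference of 0.6 is not the arm difference of about 0.1. The column may have been taken separately from the cited studies, perhaps after adjustment, and those studies are not available here. The model also leaves room for further covariates, and a null result would be read from a confidence interval based on the observed variance.

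Much of this stands. The arithmetic from 2.3 to 232 is right. The aerobic row shows that the column is not consistently a pooled SD. The documents cannot settle which SD is correct, and a wrong planning SD does not bias the analysis. The check in step 5 used complete pairs and no site effect.

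It does not justify 2.3. A two-sample t-test on different children needs the within-arm SD, and the row's own values for that are 4.2 and 3.7. An adjusted SD would be legitimate only if the plan said so and the primary analysis used the same adjustment; it does neither, and further covariates are mentioned only as a possibility. That the column has no consistent definition is itself a reason to ask for one.

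**Conclusion.** The concern holds. The 80% power for the primary outcome depends on an SD of 2.3 that conflicts with the arm SDs in the same row and has no stated source. If the arm SDs apply, power at 225 completers per arm is about 36% for 0.6 and 46% for 0.7, and the detectable difference is about 1.05. Using either arm SD alone gives 33-52%, so the conclusion does not turn on how they are combined.

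This assumes that the brackets are SDs, that the test is two-sided, that 75% of 600 children complete, and that children are independent although allocation is by house and year. The low power is conditional on the arm SDs being the relevant ones. That the row does not support its own 80% is not conditional on this.

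The one-point shortfall from 80% to 79% with SD 2.3 is a separate matter: 225 completers per arm is fewer than 232.

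**What to change.** One of two changes to the power section is needed.

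- **(a) Use the arm SDs.** Recompute the two fat-percentage rows with 3.96 and 13.15. For the primary row, restate either the power (about 36% for 0.6, 46% for 0.7) or the detectable difference (about 1.05 at 225 per arm), and note that this assumes independent children although allocation is by house and year.
- **(b) Justify the smaller SDs.** Give the source and definition of 2.3 and 11.2. If they are residual SDs after baseline adjustment, say so, state that they imply about 66% and 27% of the variance in change explained (the second is 1 - (11.2/13.152)^2), and make the primary analysis baseline-adjusted to match.

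In either case, label the brackets and state the unit of the table entries. As a minor point, check the muscle-mass row against its source or delete it: it enters a difference of 0.6 where its arm cells (0.6 and 0.5) differ by about 0.1. That row does not set the total.

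The cost is rewording, with no extra children. Under (a) the stated power or detectable difference becomes less favourable. Under (b) the sponsor must supply a source and one sentence on the primary model.

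### The muscle-mass row of the power table contradicts itself: its arm changes differ by 0.1, but its 29 per arm is derived from a difference of 0.6

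*Combined protocol and SAP*

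**What the plan says.** The power table in the section Statistic and power calculation gives, for each outcome, the change (SD) in the HIHE arm, the change (SD) in the standard arm, the difference between arms (SD) in the IG vs SG column, and a sample size. For muscle mass it prints "Muscle mass 0.6 (0.7) 0.5 (0.9) 0.6 (0.8) 29". The continuation of the table doubles 29 to 58 for the two arms and raises this to 73 to allow for missing post-tests.

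The stated basis is: "The power calculation is measured with t-test"; "The calculations are based on a power of 0.80 and p-value of 0.05"; and "The calculations are based upon a randomisation of 1:1, 50% of the participants participate in the standard program". The inputs "are based on the development on variables from the pilot study and a study with children from the same age group as on the DCSH"; the muscle-mass row is not attributed to either source. For the trial as a whole, "the total number of participants is estimated to be approx. 600 children", with losses covered by the sentence "This is under the consideration of a completion rate of 75" per cent.

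The same section names fat percentage as the primary outcome and lists aerobic fitness, health-knowledge and well-being among the most important secondary outcomes. Muscle mass is in neither place, although it is measured (Measurements, anthropometric paragraph) and falls under the statement that all outcomes will be analysed.

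**The concern.** The difference between arms should be the HIHE change minus the standard change, which is 0.6 − 0.5 = 0.1. The table prints 0.6, the same value as the HIHE arm's own change. The row therefore cannot be right as it stands, and the sample size built on it does not follow from the two arm changes beside it.

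What is at stake is how the muscle-mass result can be read. The row implies that 58 completers are enough, so that about 450 (75% of 600) would be ample. If the arm changes are the correct entries, that assurance is false, and a non-significant muscle-mass result would say little about whether HIHE has an effect of the size shown in the plan's own inputs.

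**Working it through.** **Inputs** (all from Statistic and power calculation): changes 0.6 (0.7) and 0.5 (0.9); difference 0.6 (0.8); t-test; power 0.80; significance level 0.05; 1:1 allocation; 600 children; 75% completion. Sidedness is not stated. Expected completers per arm: 600 × 0.75 / 2 = 225.

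**Step 1: reproduce the printed 29.** The normal approximation is n per arm = 2 × (1.960 + 0.842)² × (SD/difference)². With 0.6 and 0.8 it gives 28; the two-sided t-test version gives 28.9, so 29 as printed. One-sided gives 22 and does not fit. The two-sided t-test also gives 231.6 and 181.8 for the fat-percentage rows (printed 232 and 182). So the method is clear, and 0.6 was the value entered.

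**Step 2: compare each printed difference with its arm changes.**

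| Row | Difference of arm changes | Printed difference |
|---|---|---|
| Fat percentage, intervention period | −9.6 − (−8.9) = −0.7 | −0.6 |
| Fat percentage, follow-up period | 5.0 − 8.4 = −3.4 | −3.3 |
| Aerobic fitness | 148 − (−106) = 254 | 254 |
| Health-knowledge | 11.9 − 2.6 = 9.3 | 9.4 |
| Muscle mass | 0.6 − 0.5 = 0.1 | 0.6 |

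Four rows agree to within 0.1, which rounding explains. Muscle mass is out by 0.5.

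**Step 3: how far rounding can go.** A printed 0.6 can stand for 0.55 to just under 0.65, and a printed 0.5 for 0.45 to just under 0.55. The true difference then lies between just above 0 and just under 0.65 − 0.45 = 0.2.

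**Step 4: recompute, if the arm changes are right.** SD 0.8, two-sided t-test, independent children. Power is approximately Φ(difference/SD × √(n/2) − 1.960). For example, at 0.1 and n = 225: 0.125 × √112.5 − 1.960 = −0.634, and Φ(−0.634) = 0.263.

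| Difference | n per arm for 80% power | Multiple of 29 | Power at 29 per arm | Power at 225 per arm |
|---|---|---|---|---|
| 0.05 | 4020 | 139 | 5.6% | 10% |
| 0.10 | 1006 | 35 | 7.5% | 26% |
| 0.15 | 448 | 15 | 10.8% | 51% |
| 0.20 (rounding limit) | 253 | 9 | 15.5% | 75% |

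The smallest difference with 80% power at 225 per arm is 0.8 × 2.802 × √(2/225) = 0.21, just outside the range that the arm changes allow.

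**Step 5: sensitivity to the SD.** Pooling the arm SDs gives √((0.7² + 0.9²)/2) = 0.806, and power at 225 for a difference of 0.1 is still about 26%. At 0.75, the lowest SD that rounds to 0.8, it is 29%. Power at 225 passes 80% (80.6%) only if the SD is 0.75 and the difference is 0.2 at the same time, that is, with both at their rounding limits.

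**Step 6: if the printed difference is right.** An arm change must then be wrong: the standard arm would be about 0.6 − 0.6 = 0.0, or the HIHE arm about 0.5 + 0.6 = 1.1. In that case 29 per arm stands, and power at 225 exceeds 99.9%.

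**The case against.** The strongest counter-argument is that a contradiction does not show which cell is wrong. Reproducing 29 from 0.6/0.8 shows that 0.6 was the input; it does not show that 0.6 is an error. The coincidence with the HIHE arm's own change looks like a copied cell, but that is only suggestive. Nor does it settle the matter that 0.8 is close to the pooled arm SD. In three of the other four rows the SD of the difference is not the pooled one (3.96 against a printed 2.3, 13.15 against 11.2, 73.7 against 85), so the origin of that column is unclear. The source studies are not available here. This objection stands, and it makes every figure in step 4 conditional.

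A reader might infer that 29 is simply 35 times too small, or that the trial has 26% power where it claims 80%. The documents do not support either as a flat statement. Both rest on a difference of exactly 0.1, one point in a range. The second also mixes sample sizes: the plan's 80% belongs to 29 per arm, where a difference of 0.1 would give 7.5%, while 26% belongs to 225 per arm. Nor is 26% the power of the planned analysis, since Design describes a cross-over at the level of two houses and the plan specifies a covariate-adjusted mixed model.

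It is also fair to say that little depends on this row. The total of about 600 matches the primary-outcome row "Fat percentage, intervention period -9.6 (4.2) -8.9 (3.7) -0.6 (2.3) 232", which becomes 464 in total and 580 with the allowance. No section says that a null muscle-mass result would be taken as proof of no effect; that is a risk of misreading.

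**Conclusion.** The muscle-mass row is inconsistent as printed, and rounding cannot explain it: at most about 0.2 is compatible with the arm changes, a third of the 0.6 used. One of the three entries is wrong, and the documents do not say which.

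If the arm changes are right, 29 per arm is too small by a factor of about 9 at the rounding limit and about 35 at the face value of 0.1. With SD 0.8, 225 completers per arm do not reach 80% power for any compatible difference. If 0.6 is right, the sample size stands and an arm change needs correcting. The figures assume a two-sided t-test, independent children and 75% completion of 600.

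A reader might go further and conclude that the trial is too small. This row does not support that: muscle mass is neither primary nor a named key secondary outcome, and it did not set the total. Severity is minor.

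**What to change.** Check the two arm changes and the difference against the source data, correct the wrong entry and recompute the row.

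- If the difference is about 0.1, restate the row as about 1006 per arm and 2012 in total. For the recruited number, say which convention is used: dividing by the completion rate gives 2012 / 0.75 = 2683, while the table's own practice of multiplying by 1.25 (58 × 1.25 = 72.5, printed as 73; 464 × 1.25 = 580) gives 2515. Add one sentence saying that muscle mass is not a powered outcome and that 225 completers per arm give 80% power only for differences of about 0.21 or more under the simple t-test.
- If 0.6 is confirmed, correct the arm change and keep 29.

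Do not change enrolment on account of this row. The cost is one look-up in the source data, one table row and, in the first case, one sentence; no procedure changes.

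### The sample size treats children as individually randomised 1:1, but the programme is assigned to two whole houses by year, so the stated 80% power holds only if house-by-year and intake correlation are zero

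*Combined protocol and SAP*

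**What the plan says.** The section Statistic and power calculation names fat percentage as primary outcome and sizes the comparison by t-test, at power 0.80 and p-value 0.05. For the intervention period it uses a difference of 0.6 with SD 2.3 and obtains 232 per group, 464 in total. The recruitment target is about 600, with 75% expected to complete. On allocation it says: "The calculations are based upon a randomisation of 1:1, 50% of the participants participate in the standard program".

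The same section plans linear mixed models with an intervention-by-time interaction, where time means before and after the stay. The random effects are "child and site as random effects (to account for differences between children and between sites, respectively"). On covariates it adds: "Adjustment for age, sex, and possibly other covariates/confounders will also be included as fixed effects in the models".

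The allocation is described differently elsewhere. Under Design: "The design is a cross-over design at DCSH level over a two-year period with two intervention groups". Under Recruitment of participants, "it is specified that two of the DCSH change practice for one year", so that "all the children at the two DCSH are participating in the HIHE intervention, regardless of their participation in tests". It continues: "To investigate the standard program, all tests will be carried out at both of the DCSH for one year". Finally: "After the first year the two participating DCSH change intervention group".

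No section gives an intraclass correlation or a design effect, or states that such correlation is taken as nil.

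**The concern.** The unit of assignment is the house for a year, not the child. The HIHE contrast rests on two houses times two years, with different children in each of the four house-years. Children in the same house-year share staff, schedule and season, and children admitted together share a group. If either makes their changes in fat percentage alike, the 464 observations carry less information than the t-test assumes.

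Two consequences would follow. The planned test would reject a true null hypothesis more often than 5%, and a test with the right standard error would have less than 80% power. House-by-year variance also sets a limit that recruiting more children in the same four house-years cannot remove.

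The recruitment text raises a further question. It can be read as both houses running HIHE in one year and both running the standard programme in the other. Any change between the years would then be indistinguishable from the HIHE effect, and no covariate could separate the two.

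The concern is limited to HIHE versus standard. It does not touch the aim of documenting change over the stay.

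**Working it through.** **Inputs.** From the power section: difference δ = 0.6, SD s = 2.3, 600 × 0.75 = 450 completers, so N = 225 per arm and about 112 per house-year. Every correlation ρ below is an assumption and refers to change in fat percentage.

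**1. The plan's figure.** A two-sided t-test of independent children with δ = 0.6 and s = 2.3 needs 232 per arm (power 80.06%). The same formula returns the other table entries (182, 4, 100, 29), so no row contains a design effect. With 225 per arm, power is 78.8%; there is no slack.

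**2. What cancels.** Suppose the houses hold opposite programmes each year and house-years are of similar size. Each programme then appears once in each house and once in each year. Simulating the planned test (40,000 runs, 112 children per house-year):

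- ρ = 0.02, all from stable house effects: type I error 4.8%, rejection at δ = 0.6 79.1%.
- ρ = 0.02, all from shared year effects: 5.0% and 78.9%.

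These two sources do no harm.

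**3. What does not cancel: house-by-year.** The variance of the contrast is 2s²(1−ρ)/N + ρs². The planned test uses SE = s√(2/N) = 2.3 × √(2/225) = 0.2168. At ρ = 0.01 the true variance is 0.0466 + 0.0529 = 0.0995, against 0.0470 assumed, a ratio of 2.12.

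| ρ | Variance ratio | Planned test: type I error | Planned test: rejection at 0.6 | Correct-SE test: power |
|---|---|---|---|---|
| 0.001 | 1.11 | 6.3% | 77.8% | 74.7% |
| 0.005 | 1.56 | 11.6% | 74.1% | 60.1% |
| 0.01 | 2.12 | 17.8% | 71.1% | 47.7% |
| 0.02 | 3.23 | 27.5% | 67.8% | 33.7% |

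The rejection column is not valid power, because the test's size is inflated. The last column assumes the correct SE is known. If a total ρ of 0.01 is split equally among house, year and house-by-year, the simulated type I error is 9.7%.

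The term ρs² does not shrink as N grows. The correct-SE test can reach 80% only if the house-by-year SD is below 0.6/2.80 = 0.214 points, that is, ρ below (0.214/2.3)² = 0.0087.

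**4. Intake groups.** With k groups per house-year the variance is 2s²(1−ρ)/N + ρs²/k. The consent section gives information meetings every 2 to 3 weeks. If admissions follow that rhythm, k = 52/3 = 17.3 to 52/2 = 26. Ten-week blocks would give k = 5.2, which is less likely under continuous admission.

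| k | ρ | Planned test: type I error | Correct-SE test: power |
|---|---|---|---|
| 26 | 0.01 / 0.02 | 5.4 / 5.8% | 77.7 / 76.4% |
| 17.3 | 0.01 / 0.02 | 5.6 / 6.3% | 76.8 / 74.7% |
| 5.2 | 0.01 / 0.02 | 7.4 / 9.9% | 71.2 / 64.4% |

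**5. Whether the planned model helps.** With complete before/after pairs, a site intercept and the age and sex main effects drop out of the intervention-by-time contrast. Generalised least squares on 450 pairs gives an SE of 0.2168 with or without them. Adding house-by-time and year-by-time terms would leave the house-by-year interaction identical to treatment. A test on the four house-year means has 2 degrees of freedom with no house or year term (power 35% even at ρ = 0), 1 with one of them (17%) and none with both.

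**6. Same programme in both houses each year.** A shared-year ρ of 0.005, 0.01 or 0.02 gives the planned test a simulated type I error of 17.4%, 27.8% or 40.8%.

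**The case against.** The strongest reply is that the size of the harm is assumed. No correlation is documented, and the severe figures need a residual correlation of 0.01 to 0.02 in change scores after house and year effects have cancelled. At 0.001 the damage is modest. That stands as a limit on the magnitude; it does not rescue an 80% that is stated without its condition.

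The plan is also partly open about the design. It declares a house-level cross-over and includes site as a random effect, and the 1:1 wording may only be a loose allocation ratio. But the calculation itself treats children as independent. The plan does not say that site enters as an intercept only, yet a random site slope would still miss house-by-year.

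The reading with opposite programmes is the more natural one, since the design is called a cross-over and the houses swap groups. The same-programme case therefore should not drive the severity, but the two sections still need reconciling.

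The intake groups are a proxy, because meeting dates are not admission dates and stays overlap. That is why intake results are shown as a range.

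Finally, the 80% also depends on SD 2.3, while the same table row gives arm SDs of 4.2 and 3.7. With their pooled SD of 3.96, 225 per arm gives about 36% power without any clustering. That is a separate problem and does not weaken this one.

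**Conclusion.** The concern holds, and the power statement is wrong as written. The 232 per arm is correct arithmetic for a trial that randomises children; this trial assigns two houses by year. Under opposite programmes with similar house-year sizes, δ = 0.6 and SD 2.3, the stated power requires both residual house-by-year and intake-level correlation to be zero. The plan neither says so nor models either.

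The mismatch is certain; the size of the loss is not. House-by-year correlation is the serious part, because small values matter and four house-years cannot estimate it. Intake correlation costs much less. Since the primary outcome's between-programme test could exceed its nominal error rate, this needs correcting before the HIHE comparison is reported.

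**What to change.** 1. Replace the 1:1 randomisation wording with allocation by house and year. Reconcile Design with Recruitment of participants on whether the houses hold opposite programmes in the same year. If they hold the same one, state that programme is confounded with calendar year.
2. Restate 80% as power under zero residual house-by-year and zero intake-level correlation. Print results over an assumed range, for example ρ from 0 to 0.02 at each level. Name the test, and keep the planned test's type I error apart from power with the correct SE.
3. Add a random effect on change for house by admission period, with periods fixed in advance and small-sample degrees of freedom (for example Kenward-Roger). State that it covers intake clustering only.
4. State that house-by-year variance cannot be usefully estimated from four house-years, so the HIHE-versus-standard inference is conditional on its being negligible.

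The cost is wording, a small table and one model term. Entry dates are implied by the test at the start of each stay, so no new data are needed. In simulation (an analysis of intake means, 40,000 runs), if there is no clustering the term lowers power from about 79% to 74% with five periods per house-year, and to about 78% with 17 to 26. It holds type I error at 4.8 to 5.2% when clustering is at intake level only (ρ 0.01 to 0.02). With house-by-year ρ of 0.01, type I error remains about 15 to 17%, so item 4 is needed as well.

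### The allowance for 75% completion adds a quarter instead of dividing by 0.75, so neither 580 nor 600 recruits yields the 464 completers the plan requires

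*Combined protocol and SAP*

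**What the plan says.** Everything needed is in the section Statistic and power calculation of the combined protocol and SAP.

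- Outcome: "The primary outcome of the project is fat percentage".
- Error rates: "The calculations are based on a power of 0.80 and p-value of 0.05".
- Test: "The power calculation is measured with t-test".
- For fat percentage over the intervention period, the first table gives a between-group difference of -0.6 with SD 2.3, and a sample size of 232.
- The second table has two columns. The first, "Number of participants, 1:1 randomisation", doubles the per-group number to 464. The second, "Number of participants with 75% at post-tests", gives 580.
- The text then concludes that "the total number of participants is estimated to be approx. 600 children", and adds: "This is under the consideration of a completion rate of 75" per cent.

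The figure of about 600 is repeated in the section on participants and eligibility criteria and in the Design section. No other section gives a different completion rate or another rule for the allowance.

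**The concern.** A completion rate of 75% means that a quarter of those recruited are lost. The number to recruit is therefore the number of completers needed divided by 0.75, an increase of one third. The table increases each total by one quarter. That is too little, because the loss applies to the larger recruited number and not to the completers.

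The primary outcome's intervention-period row is the largest in the table and sets the recruitment total. If its allowance is too small, the planned total does not deliver the stated power even when every other planning input is accepted. Rounding 580 up to about 600 looks like a margin of 20 children. Against the correct figure it is a deficit of 19.

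**Working it through.** **Inputs**, all from Statistic and power calculation: difference 0.6, SD 2.3, significance level 0.05, power 0.80, t-test, 1:1 allocation, completion 75%. The number of sides is not stated. It is taken as two-sided because that reproduces the table; one-sided gives 182 per group by the normal approximation, not 232.

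**Step 1: reproduce the number of completers.** The normal approximation is n per group = 2 × (1.960 + 0.842)² × (2.3/0.6)² ≈ 230.7, rounded up to 231. The exact t-test calculation gives 231.6, rounded up to 232. Two groups make 464, which matches the plan. So 464 is the number needed with data, and it is correct on the plan's inputs.

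**Step 2: reproduce the allowance for incomplete follow-up.**

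| Row | Needed, N | Printed | N × 1.25 | N / 0.75 | Rounded up |
|---|---|---|---|---|---|
| Fat percentage, intervention period | 464 | 580 | 580 | 618.7 | 619 |
| Fat percentage, follow-up period | 364 | 455 | 455 | 485.3 | 486 |
| Aerobic fitness | 8 | 10 | 10 | 10.7 | 11 |
| Health knowledge | 200 | 250 | 250 | 266.7 | 267 |
| Muscle mass | 58 | 73 | 72.5 | 77.3 | 78 |

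All five printed figures follow N × 1.25 (72.5 is shown as 73). None equals N/0.75.

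**Step 3: completers and power for the primary row at 75% completion.** Completers = 0.75 × recruited. Power comes from the two-sided t-test with n = completers/2 per group and noncentrality (0.6/2.3) × √(n/2).

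| Recruited | Completers | Per group | Against 464 | Power |
|---|---|---|---|---|
| 580 | 435 | 217.5 | 29 short | 77.5% |
| 600 | 450 | 225 | 14 short | 78.8% |
| 619 | 464.25 | 232.1 | met | 80.1% |

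In recruits, the shortfall is 619 − 580 = 39 or 619 − 600 = 19.

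**Step 4: completion rate that would make the printed totals sufficient.** 464/580 = 80.0% and 464/600 = 77.3%. The plan states neither.

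**Step 5: other rows at 600.** The largest corrected requirement after the primary row is 486, so 600 still covers the remaining four rows.

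**The case against.** The arithmetic is not open to dispute, but its cause, weight and precision are.

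- **Cause.** Multiplying by 1.25 is the same as dividing by 0.80. The column is therefore also what a correct calculation at 80% completion would give, with 75% being the wrong figure. The document cannot settle which was meant. The 75% appears twice, in a column heading and in a sentence, which favours a mistaken allowance. On either reading the section contradicts itself, but the second reading adds another possible repair.
- **Size.** The operative target is about 600, not 580. The corrected 619 is 3.2% above 600 (19/600), arguably within an approximate figure, and the loss at 600 is 1.2 points of power. This stands: the effect is modest, and the 77.5% applies only if recruitment stops at 580.
- **Precision.** The primary row prints group changes of -9.6 and -8.9, which differ by -0.7, beside a printed difference of -0.6. With 0.7 and the same SD, 450 completers would give about 90% power. The planned analysis is also a mixed model with child and site effects in a cross-over at house level, not a t-test. So a restated 79% is only as good as the t-test inputs behind it. That limits how the number should be read. It does not make the allowance correct, because this check takes those inputs as given.

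**Conclusion.** The point holds. The column for 75% completion does not follow from 75% completion, and neither 580 nor 600 recruits gives the 464 completers that the plan requires for 80% power. At the planned total of 600 the shortfall is 14 completers, with power of about 79%. Keeping 80% power at 600 would need at least 77.3% completion.

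This rests on the plan's difference of 0.6 and SD of 2.3, a two-sided 5% t-test and equal groups. It does not judge whether those inputs, or a t-test without clustering or period effects, suit the design. The numerical effect is limited, but the error lies behind a headline figure of the protocol and should be corrected.

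**What to change.** Replace the second column of the second table with N/0.75: 619, 486, 11, 267 and 78. If totals must split equally under 1:1 allocation, the odd ones become 620, 12 and 268.

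Then choose one of the following and make the text agree with it:

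1. State a recruitment total of about 620, here and in the two other sections that give about 600.
2. Keep 600 and state that power for the primary outcome is about 79% at 75% completion, under the t-test assumptions of the table.
3. If 80% completion was the intended assumption, keep the column, except that the 73 for muscle mass should be checked against 72.5. Change the heading and the sentence to 80%, and say why that rate is expected.

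Options 2 and 3 change only the wording or figures of this section and leave recruitment and conduct as they are. Option 1 adds about 20 children to the target.
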